9.3 VARIABLES**9.3.1 Exposures**

Exposure to NOACs for the purpose of describing the potential study population will be identified by the presence of at least one prescription for dabigatran, rivaroxaban or apixaban.

Please refer to [Table 1 in Appendix A](#) for the corresponding codes to identify each therapy.

As described in [Section 9.11](#) Study Population, the potential study population will be divided into the following two cohorts based on NOAC exposure:

- Dabigatran vs. Rivaroxaban: July 1, 2011 to June 30, 2016
- Dabigatran vs. Apixaban: December 28, 2012 to June 30, 2016

Standard dosing for each NOAC will be used for main analyses. All doses for each NOAC will be combined for a sensitivity analysis.

9.3.2 Outcomes

The outcomes will be assessed during the post-index period for the two cohorts. If a patient discontinued the index NOAC or switched to a different NOAC, the outcomes assessment would not continue beyond the date of discontinuation or the switch. The primary and secondary outcomes assessed will be safety and effectiveness measures as described below in the [Outcomes of Interest table](#).

The safety and effectiveness analysis will be conducted for the following cohorts:

- Oral Anticoagulant treatment naive patients: Dabigatran vs. Rivaroxaban
- Oral Anticoagulant treatment naive patients: Dabigatran vs. Apixaban

Outcomes of Interest	
Primary	Stroke (hemorrhagic, ischemic, uncertain classification) Major bleeding
Secondary	Major bleeding, by the following sites 
 • Major intracranial • Major extracranial 
 ◦ Major gastrointestinal ◦ Other Stroke by type 
 • Ischemic stroke • Hemorrhagic stroke Transient ischemic attack (TIA) All-cause mortality
Further	[REDACTED]

9.3.3 Covariates

The following variables, but not limited to, will be used as covariates in the relevant analysis:

- **Gender:** Gender will be determined from eligibility file. Dichotomous variable (male=1, female=0).
- **Age:** Age in years will be determined on the index date. Continuous variable.
- **Geographic location:** Geographic locations of patient residence will be determined from eligibility file and will be grouped based on the US census classification (i.e., Northeast, Midwest, South, and West regions). South region will be the reference location.
- **Health plan type:** Health plan benefit designs such as health maintenance organization (HMO), preferred provider organization (PPO), fee-for-service (FFS), Medicare Advantage and Part D plan, etc. FFS is the reference plan type.
- **Baseline comorbid conditions:** The comorbid conditions will be captured by any inpatient claim, any two physician office visit (OV) or emergency room (ER) visits,

or a combination of both (OV+ER) with a diagnosis of the following conditions in any position during baseline (12 month pre-index period) (See [Appendix A, Table 2](#), for ICD-9-CM) and ICD-10 codes:

- Cancer
- Rheumatoid arthritis
- Coronary artery disease
- Acute myocardial infarction
- Cardiomyopathy
- Ischemic stroke
- Stroke (all types)
- TIA
- Congestive heart failure
- Left ventricular heart failure
- Hypertension
- Peripheral artery disease
- Liver disease
- Renal disease
- COPD/emphysema
- Diabetes
- Peptic ulcer (bleeding or non-bleeding)
- GERD
- Venous thromboembolism
- Hyperlipidemia
- HIV infection
- Bone marrow disease (thrombocytopenia, chronic anemia, myelofibrosis)
- Coagulopathy (hemophilia, Von Willebrand disease)
- Chronic kidney disease
- **Baseline (pre-index) medication use**
 - **Non-Oral Anticoagulants:** Number of prescription fills (normalized to a 30-day supply) will be captured during the pre-index period (See [Appendix A, Table 8](#))
 - Argatroban (can be used in procedures in lieu of heparin)
 - Unfractionated Heparin (Heparin)
 - Low Molecular Weight Heparins:
 - Enoxaparin
 - Tinzaparin
 - Dalteparin
 - Fondaparinux
 - **Other medication use:** Use of other medications will be determined if patients had ever filled a medication in the following drug classes during the pre-index period (See [Appendix A, Table 3, Table 8](#)).
 - Beta blockers
 - Calcium channel blockers
 - Diuretics
 - Other antihypertensives (i.e., angiotensin-converting-enzyme (ACE) inhibitors, combinations)

- Antihyperlipidemics
- Corticosteroids
- Antidiabetics
- Antiarrhythmics (Amiodarone HCl, Propafenone and Flecainide, Dronedarone, Betapace (Sotalol), Tikosyn, Disopyramide (Norpace), Quinidine)
- Ketoconazole
- Antiplatelets (e.g., dypidamole, aspirin, etc.)
- NSAIDs
- **Prescribing provider specialty of NOAC treatment on index date:** The prescribing specialties will include cardiology, pulmonary medicine, hematology, internal medicine, family/general practice, geriatrics, surgery (all types, including vascular surgery), gastroenterology, neurology, emergency medicine, other physician types, other non-physician specialty, unknown.
- **Baseline Charlson comorbidity index (CCI) score:** Baseline CCI measures specific individual comorbidities that are associated with mortality that are observed in the pre-index period. A score will be calculated based on CCI criteria. (See [Appendix A, Table 4](#)).
- **Baseline stroke risk:** This will be assessed during 12-month pre-index period using two alternative risk score schemes:
 - (1) the CHADS₂ stroke risk score is calculated by adding 1 point each for congestive heart failure, hypertension, diabetes, and age >75 years and 2 points for prior stroke or TIA (See [Appendix A, Table 5](#));
 - (2) the CHA₂DS₂-VASc stroke risk score - calculated by adding 1 point each for congestive heart failure/left ventricle dysfunction, hypertension, diabetes, vascular disease (prior myocardial infarction (MI), peripheral artery disease, or aortic plaque), age between 65-74, female gender, and 2 points for and age >75 years prior stroke or TIA (See [Appendix A, Table 6](#)).
- **Baseline bleeding risk:** This will be assessed during the pre-index period using the bleeding score of modified HAS-BLED (See [Appendix A, Table 7](#)).
- **Index exposure:** NOAC on the index date
- **Time to index exposure:** The time period in days between the first AF diagnosis observed in the pre-index period and the index date
- **Newly vs. Previously AF diagnosed:** patients with a claim for AF <3 months before the index date will be classified as newly diagnosed. Patients with a claim >3 months before the index date will be classified as previously diagnosed.
- **Duration of follow-up period:** The time period in days between the index date and the end of follow-up.

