2. LIST OF ABBREVIATIONS

ACE	angiotensin-converting-enzyme inhibitor
AE	Adverse Event
AF	Atrial Fibrillation
ARB	Angiotensin receptor blockers
BIPi	Boehringer Ingelheim Pharmaceuticals Inc
CDR	Clinical data repository
CHA ₂ DS ₂ -VASc	Congestive heart failure, Hypertension, Age \geq 75 years (doubled), Diabetes mellitus, Stroke (doubled), Vascular disease, Age 65–74 years, Sex category
CHADS ₂	Congestive heart failure, Hypertension, Age \geq 75 years, Diabetes mellitus, Prior Stroke or TIA or Thromboembolism
CCI	Charlson comorbidity index
CI	Confidence Interval
COPD	Chronic objective pulmonary disease
DEERS	Defense eligibility enrollment reporting system
DoD	Department of Defense
DRG	Diagnosis-related group
EMR	electronic medical record
ER	emergency room
FDA	Federal drug administration
FFS	fee-for-service
GERD	Gastroesophageal reflux disease
GI	Gastrointestinal
GIH	gastrointestinal hemorrhage
HASBLED	Hypertension, Abnormal renal/liver function, Stroke, Bleeding history or predisposition, Labile International Normalized Ratio, Elderly, Drugs/alcohol concomitantly
HIPAA	health insurance portability and accountability act
HIV	Human immunodeficiency virus

Proprietary confidential information © 2016 Boehringer Ingelheim International GmbH or one or more of its affiliated companies

HMO	health maintenance organization
████████	
ICD	International classification of diseases
ICH	intracerebral hemorrhage
IPTW	Inverse probability to weighting
IR	Incidence Rate
IRB	Institutional Review Board
████████	
KM	Kaplan-Meier
MB	Major bleed
MDR	Military health system data repository
MHS	Military health system
████████	
MTF	military treatment facilities
N	Number
NDC	National drug code
NVAF	Non-valvular Atrial Fibrillation
NOAC	Non-Vitamin K antagonist oral anticoagulant
NSAID	Non-steroidal anti-inflammatory drug
OV	office visit
PDTS	Pharmacy data transaction system
████████	
PPI	Proton pump inhibitor
PPO	preferred provider organization
PSM	Propensity score matching
PS	Propensity Score
PSTAT	Project Statistician
PY	Person-years at risk

RCT Randomized controlled trial

RR Rate Ratio

SD Standard deviation

SAS Statistical analysis software

TIA transient ischemic attack

Tx Treatment

VPN Virtual private network

[REDACTED]

[REDACTED]

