9.2 SETTING

A retrospective cohort study will be conducted using the DoD database. The target population will include OAC treatment naïve NVAF patients with at least one prescription claim for dabigatran, rivaroxaban or apixaban (new oral anticoagulant or NOAC). For each patient treated with a NOAC, the date of the first NOAC prescription (index exposure) will serve as the index date. Only those patients whose index date occurs between the respective study periods will be included. The 12-month period prior to the index date will be defined as the pre-index period. The patients will be required to have a NVAF diagnosis in the pre-index period (including index date). Inclusion and exclusion codes can be found in [Appendix B](#).

Study period NOT including pre-index period:

- Dabigatran vs. Rivaroxaban: July 1, 2011 to June 30, 2016
- Dabigatran vs. Apixaban: December 28, 2012 to June 30, 2016

Study period including pre-index period:

- Dabigatran vs. Rivaroxaban: July 1, 2010 to June 30, 2016
- Dabigatran vs. Apixaban: December 28, 2011 to June 30, 2016

NOAC approval dates used for study period determination:

- Dabigatran (Pradaxa®) – approved October 11, 2010
- Rivaroxaban (Xarelto®) – approved July 1, 2011
- Apixaban (Eliquis®) – approved December 28, 2012

Subject Inclusion Criteria:

- Age 18+ on index date
- Patients must have been prescribed either dabigatran, rivaroxaban, or apixaban identified by pharmacy claim during the study period. The first dispensing date of either study drug will be defined as the index date;
- Patients must be treatment naïve from all OAC use prior to the first NOAC prescription, during study period.
- Patients must have at least 12 months of continuous eligibility prior to the index date;
- Patients must have at least one diagnosis code of atrial fibrillation, defined as ICD-9-CM diagnosis of 427.31 or ICD-10-CM diagnosis of I48.0, I48.1, I48.2, I48.91 on the index date or during the pre-index period.

Subject Exclusion:

- Less than 12 months of continuous eligibility in the pre-index period
- Any claim for OAC drug (oral use only) in the pre-index period
- Diagnosis of hyperthyroidism during the pre-index period

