The propensity score will be defined as the probability of being treated with the index NOAC based on a set of baseline characteristics. If, for example, two patients, one in the dabigatran group and another in the rivaroxaban group, had the same propensity score, they would both have the same probability of being treated with dabigatran. The final list of baseline characteristics to be utilized in the PSM will be decided in conjunction with BI. The following baseline characteristics in the pre-index period will be considered: age, gender, health plan type, geographic region, month and year of index date, Charlson comorbidity index (CCI), stroke risk scores (i.e. CHADS₂ or CHA₂DS₂-VASc), bleeding risk scores (i.e., modified HAS-BLED), relevant baseline comorbid conditions and medication use as defined in Section 9.3.3. The distribution of baseline characteristics will be presented before and after the matching process. For baseline covariates that are not sufficiently balanced after PSM, the covariates will be included in an appropriate multivariate model to adjust for those differences.

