9.7.1 Main analysis

Patient demographics and clinical characteristics will be reported for NVAF patients by treatment groups: dabigatran, rivaroxaban, or apixaban. Stroke risk will be quantified using the CHADS₂ score, CHA₂DS₂-VASc score and bleeding risk through the HAS-BLED score. In addition, administrative variables of eligibility time and post-index follow-up time will be described. Other descriptive variables may include, but are not limited to, the following:

Comorbid conditions at baseline (the 12 month pre-index period), based on diagnosis codes:

- Cancer
- Rheumatoid arthritis
- Coronary artery disease
- Acute myocardial infarction
- Cardiomyopathy
- Ischemic stroke
- Stroke (all types)
- TIA
- Congestive heart failure
- Left ventricular heart failure
- Hypertension
- Peripheral artery disease
- Liver disease
- Renal disease
- COPD/emphysema
- Diabetes
- Peptic ulcer (bleeding or non-bleeding)
- GERD
- Venous thromboembolism
- Hyperlipidemia
- HIV infection

- Bone marrow disease (thrombocytopenia, chronic anemia, myelofibrosis)
- Coagulopathy (hemophilia, Von Willebrand disease)
- Chronic kidney disease

Medication History and Concomitant Use at baseline (the 12 month pre-index period), based on prescription information:

- **Non-Oral Anticoagulants:** Number of prescription fills (normalized to a 30-day supply) will be captured during the pre-index period (See [Appendix A, Table 8](#))
 - Argatroban (can be used in procedures in lieu of heparin)
 - Unfractionated Heparin (Heparin)
 - Low Molecular Weight Heparins:
 - Enoxaparin
 - Tinzaparin
 - Dalteparin
 - Fondaparinux
- **Other medication use:** Use of other medications will be determined if patients had ever filled a medication in the following drug classes during the pre-index period (See [Appendix A, Table 3, Table 8](#)).
 - Beta blockers
 - Calcium channel blockers
 - Diuretics
 - Other antihypertensives (i.e., angiotensin-converting-enzyme (ACE) inhibitors, combinations)
 - Antihyperlipidemics
 - Corticosteroids
 - Antidiabetics
 - Antiarrhythmics (Amiodarone HCl, Propafenone and Flecainide, Dronedarone, Betapace (Sotalol), Tikosyn, Disopyramide (Norpace), Quinidine)
 - Ketoconazole
 - Antiplatelets (e.g., dypridamole, aspirin, etc.)
 - NSAIDs

The follow-up period, which comprises the patient-time denominator, will start at index and will be censored at the first occurrence of either of the following:

- outcome event
- therapeutic switch
- index NOAC dose change

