Bleeding (includes anemia and other prior hemorrhage)	285.0x, 285.1x, 285.9x, 423.0x, 430.x-432.x, 455.2x, 455.5x, 455.8x, 459.0x, 531.0x, 531.2x, 531.4x, 531.6x, 532.0x, 532.2x, 532.4x, 532.6x, 533.0x, 533.2x, 533.4x, 533.6x, 534.0x, 534.2x, 534.4x, 534.6x, 562.02, 562.03, 562.12, 562.13, 568.81, 569.3, 569.83, 569.85, 569.86, 578.0, 578.1, 578.9, 599.7x, 719.1x, 784.7x, 786.3x; ICD-9 procedure code 44.43; CPT code 43255	D62, D64.0, D64.1, D64.2, D64.3, D64.9, I31.2, I60.xx, I61.x, I62.xx, K25.0, K25.2, K25.4, K25.6, K26.0, K26.2, K26.4, K26.6, K27.0, K27.2, K27.4, K27.6, K28.0, K28.2, K28.4, K28.6, K55.21, K57.11, K57.13, K57.31, K57.33, K62.5, K63.1, K63.81, K64.4, K64.8, K66.1, K92.0, K92.1, K92.2, M25.0xx, R04.0, R04.2, R04.81, R04.89, R04.9, R31.0, R31.1, R31.21, R31.29, R31.9, R58; ICD-10 procedure code: 0W3P8ZZ
Labile INRs		
Elderly (Age >65 years)	-	
Drug or alcohol abuse (1 point for each)	Drug: NSAIDs (GPI codes 6410, 6610), Anti-platelets (8515), Other aspirin-containing products (3940990215, 4399100222, 4399100223, 4399100232, 4399100405, 4399400321, 4399400456, 4399590415, 4399590419, 6030990225, 6499000220, 6499000221, 6499000225, 6499000226, 6499000232, 6499000320, 6499000321, 6499000335, 6499000340, 6499000450, 6499000460, 6499100220, 6499100222, 6499100228, 6499100330, 6499100335, 6599000222, 6599100210, 6599100220, 6599100325, 6599100430, 6599100510, 6599170220, 6599400220, 7599000210, 7599000240, 7599000310, 7599000320, 8515990220, 9990000000)	

	Alcohol: 291.xx, 303.xx, 305.0x, 357.5x, 425.5x, 571.1x, 571.2x, 571.3x; ICD-9 procedure codes 94.61-94.63, 94.67-94.69	F10.xxx, G62.1, I42.6, K70.xx; ICD-10 procedure code: HZ2ZZZZ, HZ30ZZZ, HZ31ZZZ, HZ32ZZZ, HZ33ZZZ, HZ34ZZZ, HZ35ZZZ, HZ36ZZZ, HZ37ZZZ, HZ38ZZZ, HZ39ZZZ, HZ3BZZZ, HZ40ZZZ, HZ41ZZZ, HZ42ZZZ, HZ43ZZZ, HZ44ZZZ, HZ45ZZZ, HZ46ZZZ, HZ47ZZZ, HZ48ZZZ, HZ49ZZZ, HZ4BZZZ, HZ50ZZZ, HZ51ZZZ, HZ52ZZZ, HZ53ZZZ, HZ54ZZZ, HZ55ZZZ, HZ56ZZZ, HZ57ZZZ, HZ58ZZZ, HZ59ZZZ, HZ5BZZZ, HZ5CZZZ, HZ5DZZZ, HZ63ZZZ, HZ83ZZZ, HZ86ZZZ, HZ88ZZZ, HZ89ZZZ, HZ93ZZZ, HZ96ZZZ, HZ98ZZZ, HZ99ZZZ
--	---	---

*the maximum score will be 8 since we do not have data available for labile INRs

After assessing the risk factors and adding up the score, the bleed risk classifications are as follows:

Score	HAS-BLED Bleed Risk Classification
0-1	Low
2	Intermediate
3 or greater	High

Table 8. Atrial Fibrillation Medications

Rate control medications	GPI codes starting with:	GPI 10
Beta blockers	3300	3310004510, 3310004512

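### Baseline NSAID, antiplatelet and similar drug use is any fill in 12 months; current use at NOAC start is not measured, so its balance is neither targeted nor verifiable

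*Combined protocol and SAP*

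**What the plan says.** Section 9.3.3 (Covariates, Other medication use) sets one rule for all listed classes: "Use of other medications will be determined if patients had ever filled a medication in the following drug classes during the pre-index period". The classes include corticosteroids, antiarrhythmics, ketoconazole, "Antiplatelets (e.g., dypidamole, aspirin, etc" and NSAIDs. Section 9.2 fixes the window: "The 12-month period prior to the index date will be defined as the pre-index period". The abstract and section 9.7.1 repeat the rule, the latter under the label "Medication History and Concomitant Use at baseline (the 12 month pre-index period), based on prescription information". For these classes no visible text asks for a recent fill, a number of fills, or supply that reaches the index date.

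Non-oral anticoagulants are treated differently in the same section. They are counted as fills normalised to 30 days of supply.

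The definition is then used in two places:

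- **Propensity score.** Section 9.7 lists among the candidate variables "relevant baseline comorbid conditions and medication use as defined in Section 9.3.3".
- **Bleeding score.** Section 9.3.3 says of baseline bleeding risk: "This will be assessed during the pre-index period using the bleeding score of modified HAS-BLED". The drug item in Appendix A, Table 7 reads "Drug: NSAIDs (GPI codes 6410, 6610), Anti-platelets (8515), Other aspirin-containing products" and has no recency rule of its own.

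**The concern.** Major bleeding is a primary outcome and is counted only while the patient is on the index NOAC. The co-medication that bears on it is therefore what the patient takes alongside the NOAC. The plan itself treats NSAIDs and antiplatelets as bleeding risks, through the HAS-BLED drug item. The 12-month flag mixes people still taking such a drug with people who stopped months before.

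Two matched arms can agree exactly on the flag and still differ in current use. The balance table would show nothing. The planned adjustment for covariates left unbalanced after matching would not be triggered, because it acts only on what is measured.

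Elsewhere the plan does attend to timing. Alternative indications and transient causes of AF use a 3-month window, and newly versus previously diagnosed AF is split at 3 months. The drugs in the plan's own bleeding score get only an ever/never flag over the full year.

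**Working it through.** **1. The plan's own figures, used as a yardstick.** Section 9.5 gives a major-bleeding rate of 3.1% per year on dabigatran, mean follow-up of 0.82 years, a two-sided alpha of 0.05, 1:1 matching and a 10% loss of dabigatran patients.

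- Event probability: 0.031 × 0.82 = 0.02542.
- Pairs: 0.9 × 16,000 = 14,400 (rivaroxaban) and 0.9 × 6,000 = 5,400 (apixaban).
- Expected dabigatran major bleeds: 14,400 × 0.02542 = 366 and 5,400 × 0.02542 = 137.

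| Comparison | Stated difference | Stated power | Two-proportion power | Log-rank (Schoenfeld) power |
|---|---|---|---|---|
| Rivaroxaban | 22% | 80% | 81.8% | 80.9% |
| Rivaroxaban | 25% | 90% | 89.9% | 89.3% |
| Apixaban | 37% | 80% | 81.6% | 81.0% |
| Apixaban | 43% | 90% | 90.7% | 90.4% |

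The stated differences reproduce, read as increases in the comparator rate. Nothing here disputes them.

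**2. How a balanced flag can hide a difference.** Let p be the any-fill prevalence, equal in both arms after matching. Let c1 and c0 be the shares of fillers in each arm who are current users at index, and HR the bleeding hazard ratio for current use. Current use is then p × c1 and p × c0, and the distortion of the hazard ratio is approximately

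[1 + p·c1·(HR − 1)] / [1 + p·c0·(HR − 1)].

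If c1 = c0 this equals 1.

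**3. Numbers.** The documents give no value for p, c1, c0 or HR, so all four are assumptions. Take p = 0.30.

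| Current share, arm 1 vs arm 2 | Current use | HR 1.5 | HR 2 |
|---|---|---|---|
| equal | equal | 1.000 | 1.000 |
| 40% vs 30% | 12% vs 9% | 1.060/1.045 = 1.014 | 1.12/1.09 = 1.028 |
| 45% vs 25% | 13.5% vs 7.5% | 1.0675/1.0375 = 1.029 | 1.135/1.075 = 1.056 |

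The range is 0% to about 5.6%.

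**4. Sensitivity to the assumptions.** With p from 0.2 to 0.5 and HR from 1.5 to 2, shares of 50% vs 40% give factors of 1.01 to 1.04, and 60% vs 40% give 1.02 to 1.08. An extreme 70% vs 30% gives 1.04 to 1.17.

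**5. Effect on the test at the top of the range in step 3.** With a factor b of 1.056, total events are 366 × (1 + b) ≈ 752 and 137 × (1 + b) ≈ 282. The shift in the log-rank statistic is √(events/4) × ln(b): 13.7 × 0.054 ≈ 0.74 and 8.4 × 0.054 ≈ 0.46. With no true difference, the two-sided 5% test would reject about 12% of the time (rivaroxaban) and 7% (apixaban). With equal shares it stays at 5%.

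**The case against.** **Nothing shows an imbalance.** A reader might infer that current use is unbalanced between the arms. The documents do not support that. Apart from a patient whose only fill falls on the index date, current users are a subset of any-fillers, so matching on the flag balances them in part. Other candidate covariates also carry information on current antiplatelet or NSAID use: coronary disease, myocardial infarction, peripheral artery disease, rheumatoid arthritis, the Charlson index, and month and year of index. The abstract adds empirically chosen diagnoses and procedures. The calculation above ignores all of these and so probably overstates the gap. This objection stands, and it limits the point to what is unmeasured and uncheckable.

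**The effect is small and the study exploratory.** Section 9.5 says the tests are to be read as exploratory, and 5.6% is well under 22% and 37%. That stands on size. It does not make the balance checkable.

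**The plan is open.** The covariate list is not exhaustive, the final propensity score list is still to be agreed, and the sensitivity analyses are redacted. That is true, but an open list permits a current-use variable without committing to one.

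**The wording conflict is weak.** One might read the abbreviation list's expansion of HAS-BLED, "Drugs/alcohol concomitantly", as contradicting the 12-month window. It only expands an acronym. The score actually used is called modified, is defined in Table 7 and is assessed over the pre-index period. Restricting its drug point to current users would also take the point away from intermittent users. So this is not evidence that the score is wrongly specified. Likewise, the label in section 9.7.1 names its own window.

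**Supply at index is not use during follow-up.** A patient may stop when the NOAC starts, or begin a week later. This is fair, and it makes the proposed flag a proxy.

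**Conclusion.** The point holds in a limited form. For NSAIDs, antiplatelets and the other listed classes, the only baseline measure is an any-fill flag over 12 months. Past users and patients with supply in hand are not separated, and the balance of current use cannot be seen. It does not apply to non-oral anticoagulants, whose fills are counted.

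Under the assumed inputs the distortion of the major-bleeding hazard ratio is 0% to about 5.6%. It can go in either direction, depending on which arm has more current users. It is below the differences the study was sized to detect, though at the upper end it would raise the false-positive rate. Every input to that range is assumed. If current shares are equal, there is no distortion. As planned, the study could not tell which case applies.

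This is a worthwhile, inexpensive improvement to a primary-outcome comparison. It is not a flaw that invalidates the design.

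**What to change.** In sections 9.3.3 and 9.7.1:

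- Keep the 12-month flag. It still catches intermittent users with no supply on the index date.
- Add a current-use flag: days supplied from a fill on or before the index date covers the index date. State that fills on the index date count, because section 9.2 ends the pre-index period before that date but includes it in the baseline period.
- Do this at least for NSAIDs and antiplatelets, the classes named in the plan's own HAS-BLED drug item. Extending it to the other classes is optional, as the documents do not tie them to bleeding.
- Enter the flag in the propensity score and show it in the balance table before and after matching.
- Leave the modified HAS-BLED drug point as defined, or vary it only in a sensitivity analysis.

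The cost is a few derived variables. Section 9.4 says drug, dose, quantity and refills are recorded, and section 9.2 already relies on calculated days supplied for the NOACs. Sample size, alpha and outcome definitions do not change. The remaining weakness is that supply on the index date only approximates use during follow-up.

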Myelofibrosis	289.83	D75.81
Coagulopathy (other and unspec)	286.9	D68.8, D68.9
Hemophilia	286.52	D68.311
Von Willebrand Disease	286.4	D68.0
Chronic Kidney Disease (not for Renal disease)	585.1	N18.1
	585.2	N18.2
	585.3	N18.3
	585.4	N18.4
	585.5	N18.5
	585.9	N18.9

Table 3. Medications of Interest (Include antiplatelets from [Table 8](#))

Description	GPI codes starting with:	GPI 10

Beta blockers	33	3310004510, 3310004512
Calcium channel blockers	34	3400000710, 3400000310, 3400001010, 3400001011, 3400001012, 3400001015, 3400001050, 3400001300, 3400001500, 3400001810, 3400001812, 3400001814, 3400002000, 3400002200, 3400002400, 3400003010
Antihypertensives	36	3610000510, 3610001000, 3610002010, 3610002510, 3610002710, 3610003000, 3610003310, 3610003510, 3610004010, 3610005000, 3610006000, 3615001020, 3615002010, 3615002420, 3615003000, 3615004020, 3615005520, 3615007000, 3615008000, 3617001010, 3620101010, 3620102510, 3620103000, 3620103010, 3620200510, 3620203010, 3620204010, 3620304000, 3625003000, 3630001010, 3630002010, 3630002500, 3640001010, 3640002000, 3640004010, 3640203010, 3660002010, 3699150220, 3699150223, 3699150270, 3699180215, 3699180225, 3699180235, 3699180240, 3699180255, 3699180260, 3699180265, 3699200210, 3699200213, 3699200220, 3699200230, 3699200240, 3699270250, 3699300205, 3699300210, 3699300270, 3699400210, 3699400220, 3699400225, 3699400230, 3699400245, 3699400250, 3699400260, 3699400270, 3699450320, 3699450345, 3699500220, 3699500270, 3699600215, 3699670210, 3699680320, 3699850250, 3699880260
Diuretics	37	3710001000, 3710001010, 3710002000, 3710003000, 3720001000, 3720002000, 3720002010, 3720003000, 3720008000, 3740001000, 3740003000, 3750001010, 3750002000, 3750002010, 3750003000, 3760001000, 3760002000, 3760002010, 3760002500, 3760004000, 3760005000, 3760005500, 3760006000, 3790003000, 3799000210, 3799000220, 3799000230, 3799200410
Antihyperlipidemics	39	3910001000, 3910001010, 3910001610, 3910002010, 3920000600, 3920002400, 3920002500, 3920002510, 3920003000, 3930003000, 3935001000, 3935002000, 3940001010, 3940003010, 3940005000, 3940005810, 3940006010, 3940006510, 3940007500, 3940990225, 3940990245, 3940990270, 3945005000, 3948005020, 3950003510, 3950004010, 3950004520, 3950005500, 3999400220, 3999400230, 3999900250

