Anticoagulants		
Dabigatran	833370302001	8333703020
Argatroban	83337015	8333701500, 8333701520
Warfarin	83200030	8320003020
Heparin	83100020	8310002020, 8310002022, 8310002025, 8310002030, (Also include HCPCS code: Injection, heparin sodium, (heparin lock flush), per 10 units - J1642 , Injection, heparin sodium, per 1000 units - J1644)
Enoxaparin	83101020	8310102010 (Also include HCPCS code: Injection, enoxaparin sodium, 10 mg - J1650)
Tinzaparin	83101080	not exist in GPI database (Include HCPCS code: Injection, tinzaparin sodium, 1000 iu - J1655)
Dalteparin	83101010	8310101010 (Also include HCPCS code: Injection, dalteparin sodium, per 2500 iu - J1645)
Rivaroxaban	83370060	8337006000
Apixaban	83370010	8337001000
Antiplatelet		
Clopidogrel	85158020	8515802010
Brilinta (ticagrelor)	85158470	8515847000
Prasugrel	85158060100330, 85158060100320	8515806010
Ticlopidine	85158080100320	8515808010
Cilostazol	85155516000320, 85155516000330	8515551600
Dipyridamole	85150030000310, 85150030000320, 85150030000330	8515003000
NSAIDs	6610	6610007000, 6610003000, 6610002000, 6610004010, 6610001010, 6610006000, 6610008000, 6610006010, 6610009010, 6610001200, 6610005000, 6610006500, 6610003500, 6610000710, 6610101000, 6610000720, 6610000800, 6610003710, 6610990220, 6610052500, 6610005200, 6610005500, 6610003010, 6610002040, 6610006050, 6610002050, 6610990328, 6610990244, 6610005260, 6610990232, 6610000700, 6610990241, 6610990340, 6610990435, 6610990337, 6610990217, 6610990338, 6610990256, 6610990440, 6610990339, 6610990315, 6610990317,

		6610990238,
--	--	-------------

Table 9. Outcome Codes

Medical Conditions	ICD-9 Codes	Description	ICD-10 Codes
Stroke		Inclusive of ischemic stroke and hemorrhagic stroke below	
Major Bleeding		Inclusive of hemorrhagic stroke, major intracranial bleeding and major extracranial bleeding below	
Ischemic Stroke (Primary Only)	433.x1	Occlusion and stenosis of precerebral arteries with cerebral infarction	I63.xxx
	434.x1	Occlusion of cerebral arteries with cerebral infarction	
	436	Acute, but ill-defined, cerebrovascular disease	I67.89
	Exclusion	EXCLUDE above codes if hospitalization lasted <48 hours and was accompanied by carotid endarterectomy (ICD-9 procedure code 38.1)	
Hemorrhagic Stroke (Primary Only)			
	431	Intracerebral hemorrhage (ICH)	I61.x

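### The antiplatelet covariate is defined to include aspirin, but its code list has no aspirin code, so aspirin is only partly adjusted for and its balance cannot be shown

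*Combined protocol and SAP*

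**What the plan says.** Section 9.3.3 defines baseline use of other medications by dispensing: "Use of other medications will be determined if patients had ever filled a medication in the following drug classes during the pre-index period". One of the classes is "Antiplatelets (e.g., dypidamole, aspirin, etc", and the codes are said to be in Appendix A, Tables 3 and 8. The abstract and Section 9.7.1 repeat the class with aspirin named.

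Table 3 has no antiplatelet row. Its title passes the class on: "Medications of Interest (Include antiplatelets from" Table 8. The antiplatelet block there contains clopidogrel, "Brilinta (ticagrelor", prasugrel, ticlopidine, cilostazol and dipyridamole. The last entry is dipyridamole ("85150030000310, 85150030000320, 85150030000330"), and the NSAID row, prefix 6610, follows directly.

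Aspirin is coded in one other place, Table 7, for modified HAS-BLED. The row "Drug or alcohol abuse (1 point for each" has a drug item that counts "Drug: NSAIDs (GPI codes 6410, 6610", then "Anti-platelets (8515), Other aspirin-containing products", followed by 40 ten-digit codes.

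The abstract says the propensity models will include the bleeding score and specified medication use. Section 9.7 says both will be considered, that the final list is to be settled with the sponsor, and that covariates left unbalanced after matching go into a multivariate model.

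**The concern.** The plan names two example drugs for this covariate. One, dipyridamole, is coded and the other, aspirin, is not. A programmer who works from the appendix will build a variable that contradicts its own definition.

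Major bleeding is a primary outcome, and the plan treats antiplatelet and aspirin use as relevant to it, both by listing the class as a covariate and by scoring it in HAS-BLED. If dispensed aspirin differs between dabigatran and a comparator, the variable meant to detect the difference cannot do so. The balance table would have an antiplatelet row with aspirin-only patients among the non-users. An imbalance in aspirin would not appear there, so the rule for post-matching adjustment would not be triggered.

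**Working it through.** **Code comparison.** The plan gives no figure for aspirin, so the check is a comparison of lists.

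- Table 7 lists 40 codes for aspirin-containing products.
- Of these, 0 match a Table 8 antiplatelet entry, by ten-digit code or by listed prefix.
- One, 8515990220, lies under Table 7's broad antiplatelet prefix 8515. Table 8 enters individual drugs instead of that prefix, so this code is missed too.
- None lies under Table 8's NSAID prefix 6610.
- One, 3940990215, lies under Table 3's antihyperlipidemic prefix 39, although it is not in the ten-digit list beside that prefix. Read by prefix, it would count as a lipid drug and not as an antiplatelet.

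**What each variable records.** A patient who fills only a listed aspirin product is *no* on the antiplatelet covariate and gains the HAS-BLED drug point. A patient who fills aspirin and an NSAID has the same drug point as one who fills the NSAID alone. A patient who fills aspirin and clopidogrel is *yes* on the covariate because of clopidogrel. The miscoding therefore affects patients with aspirin as their only antiplatelet. The drug point is then summed with the other items into a score whose maximum, per the Table 7 footnote, is 8.

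**Illustrative size.** The documents give neither aspirin prevalence by drug nor its effect on bleeding, so all inputs here are assumptions. With prevalences p1 and p0 in the two groups and bleeding rate ratio R for aspirin, and no adjustment through any other covariate:

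bias factor = (1 + p1(R − 1)) / (1 + p0(R − 1))

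- Equal prevalence, any R: 1.00
- 20% vs 15%, R = 1.5: 1.10 / 1.075 = 1.023
- 25% vs 15%, R = 1.7: 1.175 / 1.105 = 1.063

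If the comparator group has more aspirin, the factor inverts (1 / 1.063 = 0.94). The result follows the assumptions: 20% vs 30% with R = 2.0 gives 1.20 / 1.30 = 0.923.

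**Scale against sampling error.** Section 9.5 assumes 3.1% per year, 0.82 years of follow-up and a 10% loss in matching. The log-ratio standard error below assumes equal rates in both groups.

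- Rivaroxaban comparison: 16,000 × 0.9 = 14,400 per group; 14,400 × 0.031 × 0.82 ≈ 366 bleeds per group; standard error √(2/366) ≈ 0.074. ln 1.023 = 0.023 and ln 1.063 = 0.061 are about 0.3 and 0.8 standard errors.
- Apixaban comparison: 6,000 × 0.9 = 5,400 per group; about 137 bleeds per group; standard error √(2/137) ≈ 0.121. The same factors are about 0.2 and 0.5 standard errors.

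**The case against.** A reader might infer that aspirin is an unbalanced confounder of the bleeding comparison. The documents do not support that. Table 7 counts aspirin-containing products in modified HAS-BLED, and that score is planned for the propensity model. Coronary disease, myocardial infarction, peripheral artery disease, stroke and TIA are separate baseline covariates and may carry some of the same information. No aspirin prevalence by drug is given, so an imbalance after matching is possible but not shown. All of this stands. It shows partial adjustment, however, and matching on a total score does not ensure balance on one ingredient of a shared point.

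It can also be said that the specification is still open: the covariate list is not exhaustive, the propensity list is not final, and the text itself names aspirin. But choosing variables later does not repair a code list. If the antiplatelet class is chosen and coded from Table 8, aspirin is still absent. Adjustment after matching acts only on what has been measured.

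The possible bias is small beside the differences that Section 9.5 calls detectable with 80% power (22% and 37%), and that section describes the tests as exploratory. That limits the seriousness. The same section states that the aim is real-world comparative estimates, for which avoidable bias matters whatever the power.

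Finally, aspirin obtained without a dispensing record is missed under either list. That is true, but it is no reason to leave out dispensed aspirin for which the plan already has codes.

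**Conclusion.** The mismatch is certain: the covariate text includes aspirin and the list that implements it does not, although the plan holds aspirin codes elsewhere. As specified, a patient whose only antiplatelet is dispensed aspirin is recorded as a non-user. Aspirin as such is adjusted for only through the shared HAS-BLED drug point, and its balance before and after matching cannot be demonstrated.

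The consequence for the estimates is unknown. Nil to about 6% in the bleeding ratio, in either direction, rests on an assumed bleeding ratio of 1.5 to 1.7, an assumed prevalence difference of 0 to 10 points, and no adjustment through HAS-BLED or the cardiovascular covariates. Because some adjustment is planned, the true residual is likely smaller. This is a coding error worth correcting before the analysis, not evidence that the comparison is biased.

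**What to change.** - Create a baseline aspirin flag from the codes that Table 7 lists as aspirin-containing products, including 8515990220. Alternatively, add those codes to Table 8's antiplatelet block. A separate flag is cleaner, because aspirin balance can then be read directly.
- Before reuse, check for codes that also fall in another class, such as 3940990215 under antihyperlipidemic prefix 39, and state how they are counted.
- Leave 6410 as the NSAID code that Table 7 calls it; the documents do not identify it as aspirin. Reconcile its absence from Table 8's NSAID row. The documents do not describe the individual codes, so the team should confirm that the final flag covers single-ingredient aspirin.
- Enter the flag in the propensity model and report its balance before and after matching, under the same adjustment rule as other covariates.

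The cost is one more covariate and a short check of an existing code list. Aspirin without a dispensing record remains unseen, which Section 9.9 should say.
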